4.1.1 Marginal Prior for BMS-986226

Posterior information on $log(\alpha_1)$ and $log(\beta_1)$ from the monotherapy part of the study will be used as marginal BMS-986226 prior for combination with ipilimumab. This prior information is not prespecified and will be continuously updated when additional DLT information from the monotherapy is available. In the simulation (see Section 3, the prior of BMS-986226 as described in Section 1.2 (Table 1.2-1) is used for illustration purposes because no real-time DLT data are available at this time.

4.1.2 Marginal Prior for Nivolumab Parameters $(log(\alpha_2), log(\beta_2))$

Similar to BMS-986226 monotherapy in the lead-in phase, the logistic model for nivolumab is as follows:

$$logit(q_{j}) = log(\alpha_{2}) + \beta_{2}log(\frac{d_{2j}}{d_{2}^{*}})$$
, where a_{2} , $\beta_{2} > 0$.

Note that the α_2 and β_2 parameters are assumed positive, and d_2^* is the reference dose for nivolumab.

The toxicity profile of nivolumab has been studied in several studies. A bivariate normal prior for the nivolumab model parameters ($\log(\alpha_2)$, $\log(\beta_2)$) was obtained by extracting a posterior of nivolumab using incidence of treatment-related Grade 3 to 4 AEs from a Phase 1 dose-escalation study and several Phase 3 nivolumab studies, which are used later as the MAP prior for nivolumab. These include a Phase 1 dose-escalation study of nivolumab (Study CA209003, N=306 in doses of 0.1, 0.3, 1, 3, and 10 mg/kg across multiple tumor types), a randomized Phase 3 study in advanced melanoma participants progressing post anti-CTLA-4 therapy (Study CA209037, N=268 in a dose of 3 mg/kg), a Phase 3 study in previously treated participants with squamous cell NSCLC (Study CA209017, N=131 in a dose of 3 mg/kg), a Phase 3 study in previously treated participants with non-squamous cell NSCLC (Study CA209057, N=287 in a dose of 3 mg/kg), and a Phase 3
study in previously treated participants with clear-cell RCC (Study CA209025, N=406 in a dose of 3 mg/kg). The results from the simulation of nivolumab flat dose exposures, the corresponding exposure-response analyses, and review of nivolumab safety support nivolumab flat dose and the overall distributions of nivolumab exposures are comparable after treatment with either 3 mg/kg Q2W or 240 mg Q2W nivolumab.

The MAP prior for the model parameters (log(α_2), log(β_2)) was obtained in the following steps.

First, a prior distribution for nivolumab was developed:

- The median DLT rate at the reference dose (3 mg/kg every 2 weeks) was assumed to be 10%, that is, mean $(\log(\alpha_2)) = \text{logit}(0.10) = \log(0.1/0.9) = -2.197$.
- A doubling in dose was assumed to double odds of DLT, that is, mean(log(β_2)) = 0.
- The standard deviation of $log(\alpha_2)$ was set to 2, and the standard deviation of $log(\beta_2)$ to 1, which allows for considerable prior uncertainty for the dose-toxicity profile.
- The correlation between log(α₂),and log(β₂) is assumed to be 0 (assuming independence of log(α₂) and log(β₂)).
- In addition, heterogeneity between the historical study and current study was incorporated using a MAP by defining between-trial standard deviations τ_1 and τ_2 for $\log(\alpha_2)$ and $\log(\beta_2)$, respectively. The between-trial variability is assumed to be moderate. Therefore, τ_1 and τ_2 were set to follow a log-normal distribution with mean $\log(0.25)$ and $\log(0.125)$, respectively, with a common standard deviation $\log(2)/1.96$.

With this prior, the clinical trial data below were used to generate the posterior for nivolumab, which is then used as the MAP prior for this study.

Nivolumab Flat Dose (mg), Q4W	Dose of Nivolumab (mg/kg) Q2W	Toxicity ^a
	0.1	29% (5/17)
	0.3	17% (3/18)
160	1	14% (12/86)
480	3	13% (150/1146)
	10	16% (21/131)

Table 4.1.2-1:Data from Nivolumab Studies

^a % of participants with treatment-related Grade 3-4 AEs Abbreviation: Q2W = every 2 weeks; Q4W - every 4 weeks.

Table 4.1.2-2:Marginal Prior Distribution for Model Parameters for Nivolumab
(ie, Posterior from MAP Method)

Parameter	Means	Standard Deviations	Correlation
$\log(\alpha_2), \log(\beta_2)$	(-1.856, -2.131)	(0.404, 0.546)	-0.009

Note: Nivolumab prior information was based on mg/kg dosing instead of flat dosing. If real pharmacokinetic (PK) data from this study show difference from mg/kg assumption, the nivolumab prior will be revisited and modified accordingly.

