The doses of BMS-986226 for Parts B and C (combination with nivolumab or ipilimumab) will be determined using all available safety (clinical and laboratory), PK, and target engagement/PD data, as well as modeling recommendations within the Bayesian hierarchical modeling framework, ie, the BLRM-Copula model, by incorporating single-agent toxicity profiles of both BMS-986226 (Preliminary Safety Cohorts and Part A) and nivolumab or ipilimumab¹⁸ and any available combination toxicity data from Parts B and C (for subsequent doses of BMS-986226 in Parts B and C), PK/PD modeling, and will not exceed the maximum administered dose (MAD) of BMS-986226 monotherapy in the Preliminary Safety Cohorts and Part A (see Section 5.1.2.1).

At no point will the dose of BMS-986226 administered in combination with nivolumab or ipilimumab (Parts B and C) exceed the dose of BMS-986226 that has been demonstrated previously to be safe in the monotherapy dose-escalation arm (Part A), nor at any point during

combination therapy in Parts B and C will the BMS-986226 dose exceed the highest dose determined to be tolerated in the monotherapy dose-escalation arm (Part A). In addition, the starting dose level of BMS-986226 used in combination with nivolumab or ipilimumab (Parts B and C) will be one dose level lower than a monotherapy (Part A) dose that has cleared the DLT period.

Parts B and C will consist of combination dose escalation cohorts aimed to explore the kinetics of ICOS-receptor downmodulation and re-expression (and/or change in selected target engagement/PD () following administration of BMS-986226 in the presence of multiple doses of nivolumab Q4W (Part B) or ipilimumab (Q4W) (Part C). Up to 3 different doses of BMS-986226 will be administered in each of Parts B1 and C1 and an additional 6-12 participants will be enrolled in up to 3 different dose cohorts in Parts B2 and C2:

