5.1.2.2 BMS-986226 and Nivolumab Combination Therapy Cohort (Parts B1 and B2)

The purpose of combination cohort with nivolumab is to gather safety, tolerability, PK, and PD information regarding the administration of BMS-986226 in combination with nivolumab 480 mg flat dose Q4W. Part B1 aims to determine the kinetics of ICOS receptor downmodulation and reexpression (and/or change in selected target engagement/PD) following administration of BMS-986226 Q12W in combination with nivolumab 480 mg administered Q4W for a duration of 2 years. Continuous evaluation of toxicity events in the combination cohort will be performed throughout the enrollment. All participants treated with BMS-986226 in combination with nivolumab are recommended to receive premedications, as described in Section 7.1, in order to reduce the risk of infusion-related reactions.

Up to 3 different dose levels of BMS-986226 will be tested in Part B1, as determined by safety, PK and PD data. The starting dose level used in combination with nivolumab (Part B) will be one dose level lower than a monotherapy (Part A) dose that has cleared the DLT period. At each dose level, approximately 6 evaluable participants will be treated. A sentinel participant will be enrolled in Part B1 (BMS-986226 Q12W + nivolumab 480 mg Q4W) and observed for 5 days before additional participants in Parts B1 at the same dose level receive study treatment.

Part B2 (BMS-986226 Q4W + nivolumab 480 mg Q4W) will be opened at dose levels evaluated in at least one participant in Part B1. Approximately 6-12 evaluable participants will be treated per cohort, if enrolled, to better characterize safety, PK, and PD of the combination. For instance, Part B2 will begin enrollment if the re-expression of ICOS on circulating T cells is observed 4 weeks after the first dose of BMS-986226 in Parts A or B1. Part B2 would therefore be utilized to provide a more granular assessment of safety and PD of BMS-986226. More than 1 dose level (no more than 3 different dose levels) may be enrolled, should additional safety, PK, and PD data be needed.

Once the safety (during the DLT evaluation) of a combination of BMS-986226 and nivolumab has been established and a recommended BMS-986226 dose regimen has been selected for Part D, then additional participants (up to 6 additional evaluable participants) may be treated at the recommended dose to better characterize the safety, PK, and PD profile.

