5.5.3 Rationale for Ipilimumab Dose Schedule

Ipilimumab 3 mg/kg Q4W will be tested in combination with BMS-986226 during the study in Parts C1 and C2. Ipilimumab is currently approved in the US for administration in unresectable or metastatic melanoma following monotherapy administration and in combination with nivolumab at a dose of 3 mg/kg Q3W for a total of 4 doses. Ipilimumab is also approved in the US for the treatment of adjuvant melanoma at a dose of 10 mg/kg Q3W for 4 doses, followed by 10 mg/kg Q12W for up to 3 years or until documented disease recurrence or unacceptable toxicity.³⁷ Finally, ipilimumab is being studied in combination with nivolumab at various doses, including 1 and 3 mg/kg, and at dosing intervals up to Q12W. Benefit may be gained from dosing ipilimumab for a longer duration than the dosing interval of Q3W dosing for a total of 4 doses. Further, in the combination setting, less frequent dosing has shown to be beneficial to the tolerability and response profile of ipilimumab.³⁸ While ipilimumab Q4W dosing has not been tested previously, it may offer benefit to enhance the tolerability of ipilimumab versus Q3W dosing, and to allow for prolonged dosing duration versus the 4-dose schedule when administered in combination with BMS-986226.

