4.1 Prior Specification for Combination Therapy

In this section, we illustrate the prior specification of parameters in the BLRM-copula model for combination therapies. While we give prior examples for illustration purposes, all of those specifications may be subject to change when new data of monotherapies are available.

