- Data from other various Phase 2 studies (N=111 for pooled 3 mg/kg; N=325 for pooled 10 mg/kg, from Clinical Overview of a Common Technical Document for ipilimumab)

were used to generate the posterior for ipilimumab. The generation of the posterior uses the metaanalytic predictive approach, such that heterogeneity between the historical study and the current study was incorporated, by defining between-trial standard deviations $\tau 1$ and $\tau 2$ for log(α_3) and log(β_3), respectively. The between-trial variability is assumed to be moderate. Therefore, $\tau 1$ and $\tau 2$ were set to follow a log-normal distribution with mean log(0.25) and log(0.125) respectively with a common standard deviation log(2)/1.96. This leads to the MAP prior in Table 4.1.3-2.

To obtain the mixture prior, 50% weight is assigned to the MAP component, and 50% weight is assigned to the weakly informative component. The mixture prior is also presented in Table 4.1.3-2. Note that the prior of Ipilimumab is derived using mg/kg-based Q3W historical data, and the reference dose was selected to be 10 mg/kg Q3W. Since the DLT-evaluation period is 5 weeks and to be conservative, we will keep the reference dose as is when evaluating Ipilimumab as Q4W in our current study. In other words, we conservatively assume that the DLT toxicity profile in the DLT-evaluation period from Ipilimumab Q4W is similar to that for the Ipilimumab Q3W from historical studies.

Source	Dose of Ipilimumab (mg/kg*)	Toxicity (percentage [number of participants/total participants]) ⁸
Phase 3 study MDX010-20	3	20.6% (27/131)
Phase 2 Studies Pooled	3	14.4% (16/111)
	10	30.5% (99/325)
CA184169	3	18.2% (66/362)
	10	34.1% (124/364)
CA184022	0.3	9.7% (7/72)
	3	14.1% (10/71)
	10	26.8% (19/71)

Table 4.1.3-1:Data from Phase 2 and 3 Ipilimumab Studies at BMS in
Participants with Previously Treated or Untreated Advanced
Melanoma

^a % of participants with treatment-related Grade 3-4 AEs

Parameter: $(log(\alpha_3), log(\beta_3))$	Means	Standard Deviations	Correlation
Prior for Ipilimumab	(-0.827, -0.289)	(1.444, 0.787)	0.009
MAP component	(-0.805, -0.578)	(0.276, 0.232)	0.263
Weakly Informative Prior	(-0.847, 0)	(2, 1)	0

Table 4.1.3-2: Prior Distribution for Model Parameters of Ipilimumab

Note: Ipilimumab prior information was based on mg/kg Q3W dosing.

4.1.4 Prior for Interaction Parameters for Joint Toxicity of BMS-986226 and Nivolumab or Ipilimumab Combination

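### Should Part B's nivolumab prior carry the weakly informative component that Part C's ipilimumab prior has?

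*Combined protocol and SAP*

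**What the plan says.** Appendix 10 Section 4.1.2 builds the nivolumab prior "using incidence of treatment-related Grade 3 to 4 AEs from a Phase 1 dose-escalation study and several Phase 3 nivolumab studies". It allows moderate between-trial heterogeneity and then states that "the clinical trial data below were used to generate the posterior for nivolumab, which is then used as the MAP prior for this study". Table 4.1.2-2 gives the result: log(α2) has mean −1.856 and SD 0.404.

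Section 4.1.3 uses the same kind of toxicity proxy and the same heterogeneity settings for ipilimumab, then adds a step: "To obtain the mixture prior, 50% weight is assigned to the MAP component, and 50% weight is assigned to the weakly informative component".

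Both parts face the same EWOC limit in Appendix 10 Section 5: the posterior probability of a DLT rate of 33% or more must be below 30%.

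The combination priors are not presented as final. Section 4.1 says: "While we give prior examples for illustration purposes, all of those specifications may be subject to change when new data of monotherapies are available". The note under Table 4.1.2-2 adds: "If real pharmacokinetic (PK) data from this study show difference from mg/kg assumption, the nivolumab prior will be revisited and modified accordingly". On dose, protocol Section 5.1.2.2 says: "The starting dose level used in combination with nivolumab (Part B) will be one dose level lower than a monotherapy (Part A) dose". Section 5.1 says that combination doses "will not exceed the maximum administered dose (MAD) of BMS-986226 monotherapy in the Preliminary Safety Cohorts and Part A".

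**The concern.** Two partner drugs are handled by the same method up to the last step, where only one prior is made robust. On the plan's own figures the nivolumab prior is tight: its median is expit(−1.856) = 13.5%, and its 95% range is expit(−1.856 ± 1.96 × 0.404), or 6.6% to 25.7%. The upper end is below 33%. If BMS-986226 alone has shown no DLTs, the model has little left with which to explain an excess in combination except the interaction parameter, so it discounts the excess. In Part C the weak component can absorb it.

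At stake is the model's overdose check in Part B. The same DLT count in the first combination cohort could close the dose with ipilimumab and leave it open with nivolumab. Appendix 10 shows operating characteristics for monotherapy only, so a reader cannot see this.

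**Working it through.** **Inputs (Appendix 10).** BMS-986226: (log α1, log β1) with means (−0.847, 0), SDs (1.53, 1), correlation 0, reference 800 mg (Section 1.2). Nivolumab: as above, with 480 mg Q4W taken as the reference dose. Ipilimumab: MAP means (−0.805, −0.578), SDs (0.276, 0.232), correlation 0.263; weak means (−0.847, 0), SDs (2, 1); mixed 50:50, at 3 mg/kg against a 10 mg/kg reference. Interaction γ: gamma with mean 1.2 and SD 0.5, so shape (1.2/0.5)² = 5.76 and rate 1.2/0.25 = 4.8. Copula (Section 4, with m = n = 1):

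p_comb = 1 − exp(−[{−log(1−p)}^(1/γ) + {−log(1−q)}^(1/γ)]^γ)

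The posterior was computed by importance sampling with 1.5 to 3 million draws.

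**The plan's own figures first.** P(γ > 1) = 0.61, as stated. Mixture means are 0.5 × (−0.805 − 0.847) = −0.826 and 0.5 × (−0.578) = −0.289, against −0.827 and −0.289. For the monotherapy example (0/3 at 25 mg, 1/3 at 80 mg), the target probabilities are 0.36 at 200 mg and 0.30 at 80 mg, against 0.372 and 0.311. The exclusions of 400 and 800 mg and the choice of 200 mg also agree.

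**P(DLT rate ≥ 33%) after 3/6 at the starting combination dose.** The documents give no DLTs by dose, so the monotherapy histories are assumed: zero DLTs, starting dose one level below the highest cleared. Only sets within the limit of 30 DLT-evaluable participants are shown.

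| Monotherapy | Start (mg) | Part B | Part C | Part C, MAP only |
|---|---|---|---|---|
| 0/2 per level | 25, 80, 200, 400 | 0.20, 0.23, 0.27, 0.33 | 0.41, 0.43, 0.45, 0.49 | 0.20, 0.24, 0.30, 0.38 |
| 0/3 per level | 25, 80, 200, 400 | 0.16, 0.17, 0.21, 0.27 | 0.39, 0.40, 0.42, 0.45 | 0.16, 0.19, 0.24, 0.31 |
| 0/6 per level | 25, 80, 200, 400 | 0.09, 0.10, 0.13, 0.17 | 0.36, 0.37, 0.38, 0.40 | 0.10, 0.12, 0.15, 0.21 |
| 0/12 per level | 25 | 0.05 | 0.35 | 0.06 |

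Part B stays open except with 0/2 per level and a 400 mg start. Part C closes throughout. Part C on its MAP component alone behaves like Part B, so the weak component makes most of the difference. With 0/12 per level, later starts would need 36, 48 or 60 participants and cannot occur. In a set matching the 19 monotherapy participants reported in protocol Section 3.2.2.4 (assumed split 1, 1, 5, 6, 6 at 2 to 200 mg, no DLTs), Part B at 80 mg gives 0.10 after 3/6 and about 0.23 after 3/3.

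**If one monotherapy DLT occurred at 80 mg.** Section 3.2.2.4 reports a Grade 3 drug-related hypersensitivity there. Section 7.3.2 lists Grade 3 drug-related hypersensitivity among the DLTs, with an exception for infusion reactions that settle within an hour. The documents do not say how this event was classified. After 3/6 at 80 mg:

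| Monotherapy | Part B | Part C |
|---|---|---|
| 1/3 at 80 mg, 0/3 at 25 and 200 mg | 0.46 | 0.58 |
| 1/6 at 80 mg, 0/3 at 25 and 200 mg | 0.39 | 0.53 |
| 1/6 at 80 mg in the 19-participant set | 0.29 | 0.47 |

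Part B then closes, or sits just under the limit.

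**What a weak component would do in Part B.** Take the sponsor's own pre-data nivolumab prior as the weak part (log α2 mean −2.197, SD 2). Results are after 3/6 at 80 mg in the DLT-free 19-participant set:

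| Weak weight | 80 mg | 25 mg | 2 mg | Mean rate, nivolumab alone |
|---|---|---|---|---|
| 0 (as written) | 0.10 | 0.05 | 0.02 | 0.17 |
| 20% | 0.25 | 0.20 | 0.17 | 0.23 |
| 30% | 0.31 | 0.27 | 0.24 | 0.25 |
| 50% | 0.43 | 0.39 | 0.37 | 0.30 |

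At 50% every level closes down to 2 mg, because nivolumab is fixed and the model blames it. Table 4.1.2-1 has 150/1146 = 13% at 3 mg/kg. At 30% the result lies on the limit: an independent grid calculation gives 0.30 where sampling gives 0.31. At 20% the dose stays open.

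**Chance of closing at six participants (binomial tail).** The 50:50 mixture closes at 3/6. The plan as written closes at 4/6 with 0/3 per level and at 5/6 in the 19-participant set.

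| True DLT rate | ≥3 of 6 | ≥4 of 6 | ≥5 of 6 |
|---|---|---|---|
| 20% | 9.9% | 1.7% | 0.2% |
| 30% | 25.6% | 7.0% | 1.1% |
| 50% | 65.6% | 34.4% | 10.9% |

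**The case for a change.** The strongest case for a change is that the tight prior blunts the overdose rule exactly when combination data contradict the history. Half the first cohort can have DLTs without closing the dose, and at a true rate of 50% the rule closes at six participants only 11–34% of the time, against 66% with the mixture. The stated triggers for revising the nivolumab prior are pharmacokinetic differences and new monotherapy data, not combination DLTs. There is no data monitoring committee (Section 5.1.6), and the 33% aggregate toxicity rule is written for Parts D and E (Section 5.1.2.4).

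Much of this stands as description: the asymmetry is real, its cause is identified, and its rationale is unstated. It does not show that the nivolumab prior is wrong. That prior rests on 17 + 18 + 86 + 1146 + 131 = 1,398 participants, in studies that span several tumor types, and already allows for between-trial variation. The ipilimumab history is melanoma only, and on schedule Section 5.5.3 says: "While ipilimumab Q4W dosing has not been tested previously". The plan does not link these facts to the mixture, but they are ordinary grounds for borrowing less. EWOC is also not the only brake. Combination DLTs update the model, the final dose rests on overall clinical assessment, and toxicity is evaluated continuously during Part B enrollment.

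**Conclusion.** The priors differ, and the difference changes what the model says after 3/6 DLTs in most feasible DLT-free histories: 0.09 to 0.27 in Part B against 0.36 to 0.45 in Part C, with 3 or 6 monotherapy participants per level. This is a fair trade-off, not an error. Robustness in Part B would buy earlier closure of a truly toxic dose. The price is six times or more the closures at a true rate of 20%, an implausible rate for the better-characterized drug, and at 50:50 no open level at all. No tested weight is clearly right: 50% overshoots, 30% lies on the limit in the 19-participant set, and 20% leaves 80 mg open there.

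A sentence of rationale and a table of closing DLT counts for Parts B and C would help the reader, but they are detail the team can supply when it finalizes priors that Section 4.1 already treats as provisional.

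The sizes rest on assumed monotherapy data and on equating nivolumab 480 mg Q4W with the reference dose. They shrink or vanish if the 80 mg hypersensitivity counts as a DLT.

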4.1.3 Marginal Prior Derivation for Ipilimumab Parameters ($log(\alpha_3)$, $log(\beta_3)$)

Similar to BMS-986226 monotherapy in the monotherapy phase, the logistic model for ipilimumab is as follows:

$$logit(q_j) = log(\alpha_3) + \beta_3 log(\frac{d_{3j}}{d_3^*}),$$

where q_j is the probability of toxicity at dose level d_{3j} . Note that the α_3 and β_3 parameters are assumed positive, and d_3^* is the reference dose for ipilimumab.

Since DLT information from ipilimumab studies was not available, incidence of treatment-related Grade 3 to 4 adverse events (AEs) from various Phase 2 to 3 ipilimumab studies at Bristol-Myers Squibb (BMS) in participants with previously treated or untreated advanced melanoma was used in lieu of DLT rate in order to derive the prior for the BLRM parameters corresponding to the effect of ipilimumab, $(log(\alpha_3), log(\beta_3))$. Specifically, a bivariate normal MAP prior for the ipilimumab model parameters $(log(\alpha_3), log(\beta_3))$ was obtained by extracting a posterior of ipilimumab using DLT and safety data from Phase 2 and 3 ipilimumab studies in BMS and the meta-analytical-predictive approach. Finally, a mixture prior with both MAP and weakly informative components will be generated for BLRM parameters of ipilimumab.

The MAP prior for the model parameters (log(α_3), log(β_3)) was obtained in the following steps.

First, a weakly informative prior for ipilimumab was developed:

- The median toxicity rate at the ipilimumab reference dose (10 mg/kg every 3 weeks) was assumed to be 30%, ie, mean $(\log(\alpha_3)) = \text{logit}(0.30) = -0.847$.
- A doubling in dose was assumed to double the odds of DLT, ie, mean $(\log(\beta_3)) = 0$.
- The standard deviation of $log(\alpha_3)$ was set to 2, and the standard deviation of $log(\beta_3)$ was set to 1, which allows for considerable prior uncertainty for the dose-toxicity profile.
- The correlation between log(α₃) and log(β₃) was assumed to be 0 (assuming independence of log(α₃) and log(β₃)).

With this prior, the clinical trial data below (Table 4.1.3-1), including:

• Phase 3 study of ipilimumab administered at 3 mg/kg vs 10 mg/kg (Study CA184169, N=360 per arm)

- Phase 2 study of multiple doses of ipilimumab monotherapy (Study CA184022, N=71 per arm)
- Phase 3 study in HLA-A*0201 positive participants (Study MDX010-20, ipilimumab 3 mg/kg monotherapy arm with N=131)
- Data from other various Phase 2 studies (N=111 for pooled 3 mg/kg; N=325 for pooled 10 mg/kg, from Clinical Overview of a Common Technical Document for ipilimumab)

were used to generate the posterior for ipilimumab. The generation of the posterior uses the metaanalytic predictive approach, such that heterogeneity between the historical study and the current study was incorporated, by defining between-trial standard deviations $\tau 1$ and $\tau 2$ for log(α_3) and log(β_3), respectively. The between-trial variability is assumed to be moderate. Therefore, $\tau 1$ and $\tau 2$ were set to follow a log-normal distribution with mean log(0.25) and log(0.125) respectively with a common standard deviation log(2)/1.96. This leads to the MAP prior in Table 4.1.3-2.

To obtain the mixture prior, 50% weight is assigned to the MAP component, and 50% weight is assigned to the weakly informative component. The mixture prior is also presented in Table 4.1.3-2. Note that the prior of Ipilimumab is derived using mg/kg-based Q3W historical data, and the reference dose was selected to be 10 mg/kg Q3W. Since the DLT-evaluation period is 5 weeks and to be conservative, we will keep the reference dose as is when evaluating Ipilimumab as Q4W in our current study. In other words, we conservatively assume that the DLT toxicity profile in the DLT-evaluation period from Ipilimumab Q4W is similar to that for the Ipilimumab Q3W from historical studies.

Source	Dose of Ipilimumab (mg/kg*)	Toxicity (percentage [number of participants/total participants]) ⁸
Phase 3 study MDX010-20	3	20.6% (27/131)
Phase 2 Studies Pooled	3	14.4% (16/111)
	10	30.5% (99/325)
CA184169	3	18.2% (66/362)
	10	34.1% (124/364)
CA184022	0.3	9.7% (7/72)
	3	14.1% (10/71)
	10	26.8% (19/71)

Table 4.1.3-1:Data from Phase 2 and 3 Ipilimumab Studies at BMS in
Participants with Previously Treated or Untreated Advanced
Melanoma

^a % of participants with treatment-related Grade 3-4 AEs

Parameter: $(log(\alpha_3), log(\beta_3))$	Means	Standard Deviations	Correlation
Prior for Ipilimumab	(-0.827, -0.289)	(1.444, 0.787)	0.009
MAP component	(-0.805, -0.578)	(0.276, 0.232)	0.263
Weakly Informative Prior	(-0.847, 0)	(2, 1)	0

Table 4.1.3-2: Prior Distribution for Model Parameters of Ipilimumab

Note: Ipilimumab prior information was based on mg/kg Q3W dosing.

4.1.4 Prior for Interaction Parameters for Joint Toxicity of BMS-986226 and Nivolumab or Ipilimumab Combination

A gamma prior distribution for the interaction parameter γ_1 is derived to reflect the current uncertainty about the toxicity profile of the combination of BMS-986226 and nivolumab or ipilimumab. Although no PK drug-drug interaction is expected, the possibility of a significant positive interaction between BMS-986226 and nivolumab or ipilimumab cannot be totally excluded. The interaction parameter γ_1 was chosen accordingly but with a degree of uncertainty to allow for the possibility that the interaction may be positive or negative. Therefore, the following assumptions are made for the interaction parameter:

- γ_1 follows a gamma distribution and with a mean centered at 1.2, which means the combination of 2 agents is likely to have only a small synergistic effect.
- The standard deviation of γ is 0.5 such that there is a 61% prior probability that γ is larger than 1.

This model assigns the highest probability to there being small synergistic interaction and also allows for the potential of larger synergism of the toxic profiles. It also does not completely ignore the possibility of antagonism because there is a 39% prior probability that γ_1 is less than 1.

